4.3 Stopping Criteria

The DRC will oversee the safety and tolerability of AP-SA02 during the study and determine if it is acceptable to continue. However, safety and tolerability data will be reviewed on an ongoing basis by the Medical Monitor and stopping rules will be applicable starting with dosing of the first subject.

4.3.1 Criteria for Potential Interruption or Discontinuation of Study Drug in Individual Subjects

In the event that any of the following criteria are encountered, the Investigator should review the AE with the Medical Monitor as soon as feasible. The Investigator will hold the next infusion pending that review has been completed. The Investigator and Medical Monitor in consultation with the Sponsor will decide whether to continue to hold study treatment pending additional information or to discontinue study treatment.

- \geq Grade 3 AE or clinically significant laboratory abnormality per Common Terminology Criteria for AEs (CTCAE) version 5.0 considered attributable to AP-SA02 (confirmed by unblinding). If the event or laboratory test is not listed in the CTCAE, the event or laboratory test should be graded by applying the CTCAE guidelines detailed in [Section 8.1.3](#); or

Note: Clinically significant laboratory abnormalities classified per above should be confirmed with a repeat test within 24 hours.

- Clinical signs or symptoms of severe allergic or anaphylactic reaction.
- Any SAE considered to be at least possibly related to AP-SA02 (confirmed by unblinding).

Any subject who prematurely discontinues from study drug should continue to be followed per protocol for safety and key efficacy endpoints. Study staff should make every effort to complete the full panel of assessments scheduled for Early Termination of Treatment (ETOT). The reason

and date of discontinuation will be documented in the eCRF and the subject should continue to complete all safety assessments at subsequent study visits.

4.3.2 Criteria for Ad Hoc Data Review Committee Review of Study

In the event that any of the following criteria are encountered, the DRC may, as described in the DRC Charter, convene to review available data and make recommendations, including but not limited to, if the cohort should stop or pause the study, enrollment, or treatment and/or make recommendations to modify the protocol (ie, decrease or change the dose of study drug, modify safety monitoring):

Phase 1b criteria

- If any unacceptable toxicity (as determined by the Investigator or Sponsor's Medical Monitor) occurs;
- If ≥ 1 serious AE (SAE) considered attributable to AP-SA02 (confirmed by unblinding) occurs; or
- If ≥ 2 of all treated subjects experience similar SAEs or Grade 3 (CTCAE version 5.0) AEs meeting the following criteria:
 - Onset between start of dosing and 7 days after last dose; and
 - Considered attributable to AP-SA02 (confirmed by unblinding).

Note: All \geq Grade 3 (CTCAE version 5.0) laboratory abnormalities should be confirmed with a repeat test within 24 hours.

Phase 2a criteria

- If ≥ 1 serious AE (SAE) considered at least possibly attributable to AP-SA02 (confirmed by unblinding) occurs; or
- If ≥ 2 of all treated subjects experience the same or similar adverse events that are Grade 3 or higher meeting the following criteria:
 - Onset between start of dosing and 28 days after last dose; and
 - Considered attributable to AP-SA02 (confirmed by unblinding).

Note: All \geq Grade 3 (CTCAE version 5.0) laboratory abnormalities should be confirmed with a repeat test within 24 hours.

Further enrollment of subjects and dosing of the investigational product should be halted until a safety review of the event is completed. If the DRC recommends, and the Sponsor then implements, stopping study treatment and, subsequently, the Sponsor, independent of or following a DRC recommendation, proposes to restart the study, a substantial amendment will be submitted to regulatory agencies, Institutional Review Board (IRB)/Independent Ethics Committee (IEC), and Office of Human Research Oversight (OHRO). The study will not restart until the amendment has been approved by regulatory agencies and IRB/IECs. These requirements are not applicable if the Sponsor pre-emptively pauses study treatment for subject safety pending DRC review and the DRC recommends resuming study treatments and/or any study modifications recommended do not represent substantial protocol changes.

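### Protocol 4.3.2 sets the Phase 1b two-subject safety criterion at Grade 3, not Grade 3 or higher, so a pair of non-serious Grade 4 events is not counted although a Grade 3 pair is (minor)

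*Protocol*

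**What the plan says.** Protocol Section 4.3.2 says that when a listed criterion is encountered, "the DRC may, as described in the DRC Charter, convene to review available data and make recommendations". It later adds: "Further enrollment of subjects and dosing of the investigational product should be halted until a safety review of the event is completed".

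Phase 1b has three alternative criteria:

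- A judgement, with no grade or count: "If any unacceptable toxicity (as determined by the Investigator or" the Sponsor's Medical Monitor).
- One or more: "serious AE (SAE) considered attributable to AP-SA02 (confirmed by unblinding) occurs".
- At least 2 treated "subjects experience similar SAEs or Grade 3 (CTCAE version 5.0) AEs meeting the following criteria". The criteria are onset between the start of dosing and 7 days after the last dose, and attribution to AP-SA02 confirmed by unblinding.

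Three neighbouring texts use a different grade threshold:

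- The Phase 2a counterpart in the same section requires at least 2 "of all treated subjects experience the same or similar adverse events that are Grade 3 or higher meeting the following criteria".
- The note directly beneath the Phase 1b list carries a ≥ sign before "Grade 3 (CTCAE version 5.0) laboratory abnormalities should be confirmed with a repeat test within 24 hours".
- Section 4.3.1, on holding drug in an individual subject, carries a ≥ sign before "Grade 3 AE or clinically significant laboratory abnormality per Common Terminology Criteria for AEs (CTCAE) version 5.0 considered attributable to AP-SA02".

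**The concern.** The Phase 1b count names a single grade where the parallel texts name a floor. Taken as written, the more severe of two otherwise identical signals does not meet the criterion and the milder one does. Neither document gives a reason for a narrower threshold in Phase 1b, the first-in-human part of the study.

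Protocol Section 3.1 points to Section 4.3 as the place where the safety stopping rules are set in advance, and Section 4.3 applies them from the first subject dosed. This criterion is the only one in the Phase 1b list that counts non-serious events across subjects by grade. If it fails, a non-serious Grade 4 pair reaches the DRC only because someone judges that it should.

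**Working it through.** **Step 1: literal reading.** Take two treated subjects with similar, attributable, non-serious events inside the onset window. At least 2 qualifying subjects are needed.

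| Pair | Qualifying subjects as written | Met? | Qualifying subjects with *Grade 3 or higher* | Met? |
|---|---|---|---|---|
| Grade 3 + Grade 3 | 2 | Yes | 2 | Yes |
| Grade 3 + Grade 4 | 1 | No | 2 | Yes |
| Grade 4 + Grade 4 | 0 | No | 2 | Yes |

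**Step 2: does the SAE wording rescue it?** No. If either event is an attributable SAE, the one-SAE bullet is already met. The two-subject count therefore adds cases only when both events are non-serious, and that is where the wording fails.

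**Step 3: can a Grade 4 event be non-serious under this protocol?** Yes. Section 8.2 defines seriousness separately from grade. Its life-threatening criterion needs an immediate risk of death and leaves out events that could have been fatal only had they been more severe. The Grade 4 description in Section 8.1.3 that refers to life-threatening consequences is given for terms not listed in the CTCAE. Section 8.1 allows abnormal laboratory findings to be AEs.

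There is room for such findings. With 5-day dosing the onset window runs to Day 5 + 7 = Day 12. Section 8.7 schedules post-randomization draws in that window on Days 1 to 5, 7 and 12, which is 7 draws. Appendix B lists 23 chemistry + 5 hematology + 3 coagulation = 31 analytes. Most clinical Grade 4 events would be SAEs, and some laboratory events would become serious through prolonged hospitalization or as important medical events.

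**Step 4: number of subjects who can contribute.** Attribution must be confirmed by unblinding, so only active subjects count. At 3:1 allocation:

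- one cohort of 4: 4 × 3/4 = 3
- the two planned cohorts: 8 × 3/4 = 6
- Phase 1b at its ceiling of 20: 20 × 3/4 = 15

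**Step 5: size.** The documents give no event rates, so the rates below are assumptions. They refer to one event type, attributable and non-serious, with independent subjects and each subject counted at one grade: p3 at Grade 3 and p4 at Grade 4. With n = 6 active subjects,

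P(at least 2) = 1 − (1 − p)^n − n·p·(1 − p)^(n−1),

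with p = p3 as written and p = p3 + p4 as corrected. For example, at p = 0.10: 1 − 0.5314 − 0.3543 = 0.114. At p = 0.15: 1 − 0.3772 − 0.3993 = 0.224.

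| p3 | p4 | As written | Corrected | Difference (points) |
|---|---|---|---|---|
| 5% | 0.5% | 3.3% | 3.9% | 0.6 |
| 10% | 1% | 11.4% | 13.4% | 2.0 |
| 10% | 5% | 11.4% | 22.4% | 10.9 |
| 20% | 10% | 34.5% | 58.0% | 23.5 |

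Differences are taken before rounding. One result needs no assumed rate: an event type seen only at Grade 4 has p3 = 0, so the count as written is never met. All these are chances of meeting the numeric criterion, not of the DRC meeting.

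**The case against.** The strongest reply is that other routes already cover these events:

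- The unacceptable-toxicity bullet needs no count and no grade, so a single Grade 4 event can meet it. Phase 2a has no such bullet, so on that point Phase 1b is the broader of the two.
- Section 4.3.1 sends every attributable event of Grade 3 or above to the Medical Monitor and holds the next infusion. The people who judge unacceptable toxicity will therefore know of each one.
- The DRC reviews safety data through Day 12 before recommending escalation, and the Sponsor or Medical Monitor can call an ad hoc meeting. With 4 subjects per cohort, a Grade 4 pair is unlikely to be overlooked.
- Either the Investigator or the Sponsor can classify an event as serious, and subjects are inpatients through Day 7, so few Grade 4 events may remain non-serious. How the CTCAE grades listed laboratory terms is not in the documents.
- Most readers would take Grade 3 here as a floor, given the note below it and Section 4.3.1.

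Much of this stands, and it is why the point is minor. It does not remove the gap. The first route is a judgement with no stated threshold. The hold in 4.3.1 works one subject at a time and does not count across subjects. The escalation review is of blinded data by default, whereas this criterion uses unblinded attribution, and Section 3.1 lets the DRC advance cohorts simultaneously. A numeric safety criterion should not depend on readers correcting it.

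A ≥ sign lost when the PDF was read cannot be ruled out. It is unlikely, because the sign survives before the 2 in the same bullet and in the note below.

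**Conclusion.** The concern holds as a minor error in a stated decision threshold. Read literally, similar attributable non-serious pairs at Grades 3 + 4 or 4 + 4 fall outside the Phase 1b count that a Grade 3 pair meets. That conclusion rests on the text alone.

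The practical size is small and uncertain. Under the assumed rates the shortfall runs from under 1 to about 24 percentage points. The low end applies if non-serious Grade 4 events are rare; the top end needs 10% of subjects to have the same attributable non-serious Grade 4 event. That laboratory abnormalities make up most of the affected set is a reasonable expectation the documents do not establish. No automatic stop is lost, because the DRC has discretion to convene under every bullet, and protection of the individual subject is intact.

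**What to change.** First check the source page of Section 4.3.2 for a ≥ sign before Grade 3 in the Phase 1b bullet. If it is there, nothing needs to change. If it is not, reword the bullet to count similar SAEs or AEs of *Grade 3 or higher* (CTCAE version 5.0), and use the same threshold in the DRC Charter.

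The change is one phrase and adds no procedures or data. Under Section 12.1 an amendment goes through the same review and approval as the original protocol, so it is sensible to bundle it with another amendment where one is due. The possible downside is an extra ad hoc review with a short pause in enrollment and dosing.

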4.4 Withdrawal or Modification of Individual Subject Study Participation

Participation of a subject in this clinical study will be discontinued if:

- The subject or LAR withdraws consent or requests discontinuation from the study for any reason; or
- The subject becomes pregnant.

The Investigator may with concurrence of Medical Monitor or Sponsor discontinue or modify a subject's study participation for any of the following reasons:

- Occurrence of any AE (whether or not attributed to study treatment), medical condition, or circumstance that does not allow the subject to adhere to the requirements of the protocol or continued participation is not in the best interest of the subject; or
- Subject failure to comply with protocol requirements or study-related procedures.

Subjects will be considered lost to follow-up if, after completing study treatment, they fail to attend a required visit or are unresponsive despite 3 attempts to reach them by telephone, text message, email, and/or regular postal mail. Such subjects may, with the concurrence of the Sponsor, be terminated from study participation and notification sent by registered mail to the last known address. These contact attempts will be documented in both the study record and the subject's medical record.

Subjects who discontinue prematurely from the study or whose participation is modified will be strongly encouraged to complete the full panel of safety assessments scheduled for the ETOT. The reason for subject withdrawal must be documented in the eCRF.

Withdrawn or lost to follow-up subjects may be replaced to ensure adequate numbers of evaluable subjects at the discretion of the Sponsor. Subjects who discontinue for study drug-related safety or tolerability reasons will not be replaced.

4.4.1 Termination of the Study

The Sponsor may terminate the study at any time and for any reason, including but not limited to recommendation by the DRC, new non-clinical information regarding the study treatment, or if required by regulatory authorities.

Depending on the circumstances, termination procedures may or may not include completion of study treatment as assigned for all subjects who have received at least 1 dose. After a subject receives their last treatment, all EOS treatment safety evaluations will be completed.

5 STUDY TREATMENTS

[figure not shown]
5.1 Treatment Groups

The dose level of AP-SA02 to be administered to each subject will be determined based on the cohort assignment. [Table 1](#) shows the dosage (in PFU) per cohort. The dose level to be tested in the Phase 1b additional cohort(s) (up to 3) and Phase 2a will be based on the observed safety and tolerability in the prior dosed subjects.

Table 1. Dosage per Cohort

Phase Cohort	Each Dose (Approximate PFU/phage)	Each Dose (Approximate Total PFU)	Total Daily Dose (Approximate Total PFU)	Total Dose Over 5 Days (Approximate Total PFU)
Phase 1b				
1	1×10^9	2×10^9	8×10^9	4×10^{10}
2	1×10^{10}	2×10^{10}	8×10^{10}	4×10^{11}
Phase 2a	TBD	TBD	TBD	TBD
PFU = plaque-forming units; TBD = to be determined.				

5.2 Rationale for Dosing

5.3 Randomization and Blinding

Subjects in Phase 1b will be randomized in a 3:1 ratio in a blinded manner to receive AP-SA02 or placebo. For Phase 2a, subjects will be randomized in a 2:1 ratio in a blinded manner to receive AP-SA02 or placebo.

Subjects will be randomized using a centralized randomization system, according to a computer-generated randomization list, and stratified by methicillin susceptibility/resistance for Phase 2a only. Dosing should occur as soon as possible after randomization. Treatment group assignment will be blinded to the subjects, site study team, Sponsor study team, Contract Research Organization (CRO) study team, and Investigators.

5.4 Breaking the Blind

Unblinding at the request of the Investigator should occur only in the event of severe AE or SAE that is reasonably assessed as treatment related and for which it is necessary to know the treatment assignment to determine an appropriate course of therapy for the subject. If the Investigator must identify the treatment assignment of an individual subject, the Investigator or qualified designee should request the treatment assignment from the centralized randomization system. They should not attempt to get this information from the site's unblinded study team. The Investigator is advised to not reveal the treatment assignment to any other site, Sponsor, or CRO personnel.

Whenever possible, prior to proceeding with unblinding, the Investigator will contact the Sponsor to discuss the need to break the blind. The Investigator will notify the Sponsor as soon as is practical in the event of the study blind being broken and will document the reason. In the event this is not possible, the Investigator should contact the Sponsor as soon as possible to discuss the event without revealing the treatment assignment. The Investigator must document the subject identification, the date and time of breaking the blind, and must clearly explain the reasons for breaking the blind.

Medically necessary care should not be delayed for unblinding information (ie, the Investigator should treat the subject based on the subject's signs/symptoms without waiting for the unblinding process to be completed).

Subjects who are unblinded and discontinue study drug should continue to complete all safety assessments at subsequent study visits.

5.5 Drug Supplies

5.5.1 Formulation and Packaging

Study drug will be labeled according to local regulatory requirements.

Placebo will be a sterile dilution buffer used for active AP-SA02 [REDACTED]

5.5.2 Study Drug Preparation and Dispensing

5.5.3 Study Drug Administration

AP-SA02 or placebo will be administered via IV bolus infusion every 6 hours for 5 consecutive days in an inpatient location, unless the dose, frequency, or duration is modified after DRC review. For a delayed dosing administration, if the dose is delayed by <2 hours, the original schedule, relative to the first dose of study drug should be kept. If dose administration is delayed by >2 hours, the next dose, and all subsequent doses, should be based on the timing of the delayed dose and subjects should receive all study drug doses, even if this extends the treatment period. Sites should complete dose administration within \pm 30 mins of the scheduled dose administration time. In addition, all subjects will receive at least 14 days (uncomplicated SAB) or 28 days (complicated SAB) and up to 56 days of BAT. BAT will be administered at the discretion of the Investigator.

Subjects must be directly observed during study drug/placebo administration by clinical personnel. The first dose of study drug on Day 1 must occur as close as possible to the time of randomization.

5.5.4 Treatment Compliance

Details of the date and time when the study drug is administered, along with any deviation from the procedure described in this protocol, will be recorded in the subject's source documents and the eCRF.

5.5.5 Storage and Accountability

The Investigator will agree to not supply the study drug to any person other than the sub-Investigators, designated study staff, and the subjects participating in the study.

The Investigator will return or destroy all study drugs according to the Pharmacy Manual. The list of destroyed vials must be recorded. The Investigator must agree to neither dispense the study drug from, nor store it at, any study site other than the study site agreed upon with the Sponsor. Details on study drug accountability and destruction will be included in the Pharmacy Manual.

5.6 Prior and Concomitant Medications and/or Procedures

5.6.1 Excluded Medications and/or Procedures

The following medications and/or procedures are prohibited:

- Any investigational treatment within 28 days of Screening; and
- Anticipated requirement for effective systemic bacterial therapy unrelated to the treatment of SAB or other planned use of systemic antibacterial therapy (eg, treatment of acne vulgaris).

Note: Prophylactic antibiotics for operative dental procedures and chronic suppressive oral antibiotic therapy after completion of a minimum of 14 days (uncomplicated SAB) or 28 days (complicated SAB) to 56 days of BAT are permitted.

5.6.2 Documentation of Prior and Concomitant Medication Use

Any treatment given in addition to the study drug during the study will be regarded as a concomitant medication and must be recorded on the appropriate eCRF.

Any relevant medications received in the 28 days prior to randomization must be recorded on the appropriate eCRF, along with the reason for use, dates of administration, and dosages.

Concomitant medications, including over-the-counter medications and herbal supplements, should be kept to a minimum during the study. However, if these are considered necessary for the subject's welfare and are unlikely to interfere with the study drug, they may be given at the discretion of the Investigator and recorded in the subject's source documents and the eCRF.

6 STUDY PROCEDURES

Study procedures will follow the Schedule of Procedures ([Appendix A](#)).

7 EFFICACY ASSESSMENTS

7.1 Phase 1b Multiple Ascending Dose Safety Endpoints

The primary endpoint is safety. Safety will be evaluated by presenting summaries of the following:

- Treatment-emergent AEs (TEAEs), which are defined as AEs occurring after the first dose of study drug through TOC for study drug (Day 12) or through EOS for SAEs;
- Vital signs; and
- Clinical laboratory evaluations.

The endpoints listed in [Section 7.2](#) for Phase 2a may be assessed as secondary endpoints in the safety cohorts; however, these cohorts are exploratory and not powered for any efficacy variable.

7.2 Phase 2a Endpoints

The Phase 2a endpoints are the following:

- Time to reach a NEWS2 score ≤ 2 maintained for at least 24 hours or hospital discharge (whichever comes first) for subjects on active drug versus placebo in the Microbiological Intent-to-Treat (MITT) Population;
- Clinical Improvement or response at TOC for study drug (Day 12) in the MITT Population;
- Proportion of subjects reaching a NEWS2 score ≤ 2 maintained for at least 24 hours or hospital discharge (whichever comes first) for subjects on active drug versus placebo at TOC for study drug (Day 12) in the MITT Population;
- Microbiological outcome at EOT for study drug (Day 5);
- Clinical Improvement or response at TOC for BAT (7 days [± 1 day] after the end of BAT);
- Clinical Improvement or response at EOS (28 days after the end of BAT);
- Time to death;
- NEWS2 score while hospitalized by study day;
- Late composite efficacy, as defined by the following:
 - Survival at EOS (Days 39 to 81); and
 - No evidence of microbiological failure, as defined by either of the following:
 - Blood cultures that remain positive for SA ≥ 7 days from randomization; or
 - Isolation of SA from the blood or another sterile site (eg, joint fluid, tissue) > 14 days from randomization.

- Microbiological failure or relapse by any of the following:
 - Blood cultures that remain positive for SA ≥ 7 days from randomization;
 - Isolation of SA from the blood or another sterile site (eg, joint fluid, tissue) >14 days from randomization; or
 - Blood culture positive for SA >72 hours after the first blood cultures showing CL of SAB (defined as 2 consecutive days with negative SA blood cultures).
- Time to resolution of SAB;
- Time to hospital discharge (and time to hospital discharge readiness);
- Need for and duration of intensive care unit stay;
- Need for and duration of endotracheal mechanical ventilation;
- Need for and duration of noninvasive pressure ventilation (eg, Continuous Positive Airway Pressure, Bilevel Positive Airway Pressure);
- PK of AP-SA02 with IV administration;
- Relationship between AP-SA02 exposures and safety and efficacy endpoints;
- Immunogenicity of AP-SA02 at EOS;
- Time to resolution of any signs and/or symptoms of bacteremia present at Screening;
- Time to resolution of any signs/symptoms related to focal site of SA infection (eg, joint pain; redness; swelling; weight-bearing, back pain; weight-bearing, skin redness; drainage) from randomization on Day 1;
- TEAEs, which are defined as AEs occurring after the first dose of study drug through TOC for study drug (Day 12) or through EOS for SAEs;
- Proportion of subjects with acute kidney injury (AKI), defined as stage 1 or higher using modified Risk-Injury-Failure-Loss-End-stage renal disease (RIFLE) criteria ([Appendix D](#)) at any time within the first 7 days or new need for renal replacement therapy between Day 1 and EOS;
- Vital signs;
- Clinical laboratory evaluations;
- Change in CRP from baseline to EOS;
- Change in IL-10 from baseline through TOC for study drug (Day 12);
- Change in SA isolate sensitivity to AP-SA02 between initiation of study drug and the last isolation of SA from a sterile site (blood, joint fluid, tissue);
- Change in SA isolate susceptibilities to anti-staphylococcal antibiotics from baseline;
- Change in SA isolate susceptibility to BAT from baseline; and
- Clinical and microbiological outcomes by foci of infection.

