8.9 Vital Signs

Vital signs will be measured at Screening, prior to infusion (-1 hour window) daily on Day 1 through Day 7, TOC for study drug (Day 12), TOC for BAT, and EOS. Vital signs will include temperature, heart rate, and blood pressure. Vital signs will be obtained at every visit unless the subject has been discharged and visits are being performed remotely. During the Treatment Period, vital signs should be obtained prior to each infusion (-1 hour window). Wherever possible, vital signs will be obtained after at least 5 minutes resting in a supine or sitting position. If more than 1 measurement is taken on a given day, the highest value for temperature should be recorded in the eCRF.

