Late composite efficacy will be assessed programmatically based on the blood cultures tested by local microbiology laboratories per the definition in [section 2.3.2](#) at EOS. Proportion of subjects who experience late composite efficacy will be provided. Chi-square test p-value will be provided for the counts of subjects who experience late composite efficacy to compare AP-SA02 and placebo.

Microbiological failure or relapse will be assessed programmatically based on the blood cultures tested by local microbiology laboratories per the definition in section 2.3.2. Proportion of subjects who experience microbiological failure or relapse at TOC for study drug (Day 12), TOC for BAT (7 days [ $\pm 1$  day] after the end of BAT) and EOS (28 days after the end of BAT) will be provided.

If subjects have microbiological failure or relapse at TOC for study drug (Day 12) and negative blood cultures after Day 12, then subjects will not be included as microbiological failure or relapse at TOC for BAT (7 days [ $\pm 1$  day] after the end of BAT) or EOS (28 days after the end of BAT). If subjects have microbiological failure or relapse at TOC for BAT (7 days [ $\pm 1$  day] after the end of BAT) and negative blood cultures after TOC for BAT, then subjects will not be included as microbiological failure or relapse at EOS (28 days after the end of BAT). Chi-square test p-value will be provided for the counts of subjects who experience microbiological failure or relapse to compare AP-SA02 and placebo.

Time to death will be analyzed. Subject alive will be censored at the last date to be known alive.

$$\text{Time to death (days)} = \text{Censoring date/death date} - \text{date of first dose of study drug} + 1$$

The Kaplan-Meier method will be used to estimate the 25%, median and 75% times. The hazard ratio, 95% confidence interval (CI) of hazard ratio, and p-value from Cox regression model will be provided to compare AP-SA02 and placebo. Cox regression will include treatment (AP-SA02 and placebo) as factor.

Time to hospital discharge (and time to hospital discharge readiness) will analyzed. The subjects who will be in the hospital during the study will be censored at the date of last visit.

- Time to hospital discharge (days) = Censoring date/first hospital discharge date – date of first dose of study drug + 1
- Time to hospital discharge readiness (days) = Censoring date/first hospital discharge readiness date – date of first dose of study drug + 1

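### Late-composite success and freedom from failure or relapse need no negative culture, so a survivor who missed the mandated late cultures scores the same as one with documented negatives

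*Protocol*

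**What the plan says.** Protocol Section 7.2, repeated in SAP Section 2.3.2, gives the late composite two parts. The first is being alive at EOS (Days 39 to 81). The second is "No evidence of microbiological failure, as defined by either of the following", followed by two limbs: blood cultures still positive 7 or more days after randomization, or S. aureus isolated from blood or another sterile site more than 14 days after randomization. The separate failure-or-relapse endpoint uses the same two limbs and adds a third: "Blood culture positive for SA >72 hours after the first blood cultures showing CL of SAB".

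SAP Section 3.4.1 states: "Late composite efficacy will be assessed programmatically based on the blood cultures tested by local microbiology laboratories per the definition". For the other endpoint it states: "Microbiological failure or relapse will be assessed programmatically based on the blood cultures tested by local microbiology laboratories". Failure or relapse is reported at TOC for study drug, TOC for BAT and EOS. A chi-square p-value comparing the arms is given for both endpoints. The section contains no rule, category or denominator for a subject without a culture. SAP Section 3.1.5, on missing data, covers only dates of adverse events and medications.

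Protocol Section 7.7 and footnote q of the Schedule of Procedures require blood cultures regardless of clinical indication at Day 1, Day 5, Day 7, Day 12, TOC for BAT and EOS. Two of these fall after Day 14: TOC for BAT (Days 18 to 60) and EOS (Days 39 to 81).

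**The concern.** Both endpoints treat the absence of a positive culture as a good result. For a subject who was cultured and found negative, that is evidence of sustained clearance. For a subject who was not cultured, it is no evidence, yet the score is the same. Survival can be learned without a blood draw, so the survival part of the composite does not protect against this.

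At stake is what the late results can support. A late success rate would mix documented clearance with missing data, and a difference between arms could partly reflect which arm missed more cultures. Because the plan is silent, the handling could also be settled after the data are known.

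**Working it through.** **The plan's own figure.** The only power statement (Protocol 9.2.6, SAP 2.2.4) concerns clinical response at Day 12: 30% against 80%, 38 MITT subjects, 2:1, one-sided 0.05, Fisher's exact test, at least 80% power. By exact enumeration the power is 87.8% at 25:13 and 86.3% at 26:12, so the statement is met. It concerns another endpoint and is used here only for planning arm sizes: 42 × 0.90 = 37.8, about 38; 38 × 2/3 = 25.3 and 38 × 1/3 = 12.7, about 25 and 13.

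**Tracing the definition.** Take two survivors, both culture-negative on Days 5, 7 and 12. A has negative cultures at TOC for BAT and EOS; B has none after Day 12.

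| Element | What triggers failure | A | B |
|---|---|---|---|
| Alive at EOS | death | alive | alive |
| Still positive at ≥7 days | positive culture | not met, tested | not met, tested |
| Isolate after >14 days | positive culture | not met, tested | not met, **untested** |
| Relapse >72 hours after clearance | positive culture | not met, tested | not met, tested only to Day 12 |
| Late composite | | success | success |
| Failure or relapse at TOC for BAT and EOS | | no | no |

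**Do neighbouring rules cover B?** Clinical outcome has an indeterminate class (Protocol Table 2). Microbiological outcome has presumed eradication and presumed persistence for cultures not done (Protocol Table 5, SAP Table 3). Neither is linked to these two endpoints. SAP 3.4.1 does use later negative cultures, but only to clear an earlier failure at later visits; a subject who never failed needs none.

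**Illustration of size.** The documents give no rate of missed late cultures and no late failure rate. All rates below are assumptions, with missingness independent of true outcome within each arm. Let m be the share without late cultures, p the true success rate and f = 1 − p the undetected failure rate among those missing.
- Missing counted as success: observed rate = p(1 − m) + m, an overstatement of m × f.
- Missing counted as failure: observed rate = p(1 − m).

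1. m = 0.20, f = 0.10 to 0.30: 0.20 × 0.10 = 0.02 and 0.20 × 0.30 = 0.06, so **2–6 points** per arm. That is 0.20 × 25 = 5 and 0.20 × 13 = 2.6 (about 3) subjects scored without late evidence.
2. True rates 80% and 60%, m = 0.20 in both arms: 0.80 × 0.80 + 0.20 = 84% and 0.60 × 0.80 + 0.20 = 68%. The difference shrinks from 20 to **16** points.
3. Equal true rates, m = 0.30 against 0.10, f = 0.10 to 0.30. Missing as success: (0.30 − 0.10) × f = **2–6** points in favour of the arm with more missing. Missing as failure: (0.30 − 0.10) × (0.70 to 0.90) = **14–18** points against that arm.
4. True rates 80% and 60%, m = 0.30 against 0.10. Missing as success: 86% − 64% = **22** points. Missing as failure: 56% − 54% = **2** points.
5. One subject is worth 1/25 = **4.0** points on AP-SA02 and 1/13 = **7.7** points on placebo.

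**The case against.** Several points on the other side stand.

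- **Remote visits.** A reader might infer that the protocol lets late cultures lapse once subjects go home. It does not. Protocol Section 8.9 reads: "Vital signs will be obtained at every visit unless the subject has been discharged and visits are being performed remotely". That concerns vital signs only. Late cultures are mandated, and the schedule also places a physical examination, ECG and laboratory bloods at both late visits. The gap arises from missed mandated cultures.
- **Untested altogether.** A reader might infer that such a subject succeeds with no testing at all. Survival at EOS must be known, the Day 7 and Day 12 cultures bear on persistence, relapse can be shown before Day 14, and clinically prompted blood or sterile-site cultures may detect symptomatic relapse.
- **Bias toward the drug.** A reader might infer a built-in advantage for AP-SA02. Assignment is blinded, nothing in the documents predicts more missed cultures in one arm, and equal missingness shrinks a true difference (step 2).
- **Missing equals success is not stated.** This is true; it follows from applying the definition literally. Programming specifications sit in a separate document that may contain a rule, but neither the protocol nor the SAP does.
- **Other outputs.** Microbiological and clinical outcomes at the same visits, and subject listings, will show some absent cultures, though not within these two endpoints.
- **Weight.** These are two of many unranked endpoints, and SAP Section 3.1.4 plans no formal testing.

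These points narrow the concern. They do not supply a rule for a survivor without a late culture.

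**Conclusion.** The concern holds in a limited form. The definitions, derived by program, give a survivor who missed the late cultures and had no earlier failure the same result as a survivor with documented negative cultures. This is more than omitted detail, because the plan provides for missing data in the neighbouring endpoints and not here.

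The size is unknown. The 2–6 points per arm rest on an assumed 20% missing and 10–30% undetected failure. An overstatement of the full 20 points would require every untested survivor to have failed, which nothing in the documents suggests. Step 4 shows that with unequal missingness the unstated rule can matter more than the effect being estimated. The endpoints are supportive, so this is a change that should be made, not one on which the trial depends.

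**What to change.** In SAP Sections 2.3.2 and 3.4.1, before database lock:

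- Classify each subject as success, failure or not assessed for the late composite, and likewise for failure or relapse at TOC for BAT and at EOS.
- Require, for success or for no failure or relapse at a given visit, at least one valid S. aureus-negative blood culture from that visit's window or later. A negative culture taken merely after Day 14 would not be enough, because it could precede both late visits.
- Keep deaths (for the composite) and positive cultures as failures. Survivors without the required culture are not assessed.
- Report the not-assessed count by arm, and show the proportions and the between-arm difference twice, with that class counted as success and as failure.

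Counting not-assessed subjects as non-successes should not be the sole main analysis: with unequal missingness it can distort the difference more than the present rule does (step 3).

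The cost is SAP wording, one derived flag and a second set of summaries. No visit or procedure changes. The downside is slightly more analysis work and a wider, less favourable range for the late success rate.
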